All non-substantial/ minor/ administrative amendments should be submitted to the IRB as per country specific requirements. In some countries pre-approval of a minor amendment is not required and will just be held on file by the sponsor and investigator.

	Document Name	Clinical Protocol 207587		
	Type	Version	Document Identifier	Effective Date
	eldo_clinical_doc	2.0; Most-Recent; Effective; CURRENT	090032d580d16e68	24-Mar-2017 07:31:59
	Reason For Issue	Auto Issue		

PROTOCOL AMENDMENT PAGE

Details of all amendments should be recorded in the table below. Affected sections should be listed in the table; the actual amendment/ change should be made in the relevant section of the main protocol.

To highlight the change, the following features will be used:

To **add** text: Use of **CAPITAL LETTERS, BOLD AND UNDERLINE**

To **delete** text: Use of Strikethrough e.g. ~~strikethrough~~

Amendment No. & New Protocol Version No.	Type of Amendment	Reason for Amendment	Other Documents Requiring Amendment	Section(s) Amended	PI Amendment Agreement Signature & Date
Amendment No.: 1	Non-Substantial/Minor 	Correction to errors in text to reflect the schedule of events and details in main sections; patch sites will be assessed 48 hours after patch removal and irradiations on Tuesdays in the Induction Phase. Clarify wording: AND ONCE FOR FINAL INDUCTION PHASE PATCH GRADING/ASSESSMENT ON THE FIRST DAY OF THE REST PHASE (VISIT 14/DAY 22) Clarify wording that if a	Informed Consent  Yes  No Safety Statement  Yes  No CRF  Yes  No	SYNOPSIS: Brief Summary and Study Design 3.1 Study Design Study Design 3.1 Study Design 3.1 Study Design	Signature:
Protocol Version No.: 2.0	Substantial/ Major 				Date:

 GlaxoSmithKline	Document Name	Clinical Protocol 207587		
	Type	Version	Document Identifier	Effective Date
	eldo_clinical_doc	2.0; Most-Recent; Effective; CURRENT	090032d580d16e68	24-Mar-2017 07:31:59
	Reason For Issue	Auto Issue		

		subject develops a combined irritation score of 3 or greater during the Induction Phase, the site will not be irritated, a new patch will be applied to a naïve site, which will be irritated following removal 24 hours later and per the schedule of events.		3.4 Study Design and application Amount Justification 6.2.2 Patch Assessment 12.2 Appendix 2	
Amendment No.:	Non-Substantial/Minor 		Informed Consent  Yes  No Safety Statement  Yes  No CRF  Yes  No		Signature:
Protocol Version No.:	Substantial/ Major 				Date:
Amendment No.:	Non-Substantial/Minor 		Informed Consent  Yes  No Safety Statement  Yes  No CRF  Yes  No		Signature:
Protocol Version No.:	Substantial/ Major 				Date:
Amendment No.:	Non-Substantial/Minor 		Informed Consent  Yes  No Safety Statement  Yes  No CRF  Yes  No		Signature:
Protocol Version No.:	Substantial/ Major 				Date:

 GlaxoSmithKline	Document Name	Clinical Protocol 207587		
	Type	Version	Document Identifier	Effective Date
	eldo_clinical_doc	2.0; Most-Recent; Effective; CURRENT	090032d580d16e68	24-Mar-2017 07:31:59
	Reason For Issue	Auto Issue		

SCHEDULE OF EVENTS

Study Phase	Screening	Induction												Rest	Challenge				
Study Week	-	Week 1				Week 2				Week 3				Week 4-5	Week 6				
Procedure/ Assessment	VISIT 1 DAY -14 to DAY 0	VISIT 2 DAY 1	VISIT 3 DAY 2	VISIT 4 DAY 4	VISIT 5 DAY 5	VISIT 6 DAY 8	VISIT 7 DAY 9	VISIT 8 DAY 11	VISIT 9 DAY 12	VISIT 10 DAY 15	VISIT 11 DAY 16	VISIT 12 DAY 18	VISIT 13 DAY 19	VISIT 14 DAY 22	VISIT 15 DAY 36	VISIT 16 DAY 37	VISIT 17 DAY 38	VISIT 18 DAY 39	VISIT 19 DAY 40
Day of Week	-	Mon	Tue	Thu	Fri	Mon	Tue	Thu	Fri	Mon	Tue	Thu	Fri	Mon	Mon	Tue	Wed	Thu	Fri
Informed Consent	X																		
Demographics	X																		
Medical History	X																		
Current/Concomitant medication review	X	X	X	X	X	X	X	X	X	X	X	X	X	X	X	X	X	X	X
Fitzpatrick Skin Type Assessment	X																		
Inclusion/Exclusion Criteria	X	X ^a																	
Dermatologist Assessment ^a	X	X																	X
Subject Eligibility	X	X																	
Continued Eligibility		X	X	X	X	X	X	X	X	X	X	X	X	X	X	X	X	X	X
Randomisation		X																	
Patch Application		X ^b		X ^b		X ^b		X ^b		X ^b		X ^b			X ^c				
Patch Removal			X ^d		X ^d		X ^d		X ^d		X ^d		X ^e			X			
UVA Irradiation			X		X		X		X		X		X			X ^f			
Grading/Assessment of the patch sites		X ^g	X	X	X	X	X	X	X	X	X	X	X	X ^h	X ⁱ	X	X ^j	X ^j	X ^j
Adverse Events ^k		X	X	X	X	X	X	X	X	X	X	X	X	X	X	X	X	X	X
Study Conclusion/ Exit from Study/																			X

 GlaxoSmithKline	Document Name	Clinical Protocol 207587		
	Type	Version	Document Identifier	Effective Date
	eldo_clinical_doc	2.0; Most-Recent; Effective; CURRENT	090032d580d16e68	24-Mar-2017 07:31:59
	Reason For Issue	Auto Issue		

Note: Visit 1 and Visit 2 could occur on the same day but Visit 2 must be within 14 days of Visit 1.

- a. Performed by a qualified dermatologist (Inclusion criteria 3c)
- b. Subjects will report to the study site 12 times during the Induction Phase - 6 patch application visits – patches will be applied Mondays and Thursdays. The patches will remain in place for 24 hours during the week.
- c. Challenge Phase Patch application (Visit 15/Day 36) - 2 patches will be applied to naïve (virgin) skin sites. The patches will remain in place on the naïve sites for 24 (± 2) hours and will be evaluated at 30 minutes (up to 1 hour) after patch removal and again at 24 (± 2), 48 (± 2) and 72 (± 2) hours after patch removal (e.g., apply the patches on Monday, remove the patches on Tuesday, and evaluate the sites on Wednesday, Thursday and Friday. (Challenge Phase)
- d. 30 minutes (up to 1 hour) after each removal of the patches, a trained blinded assessor will perform an assessment of all test sites for irritation symptoms using the scoring system detailed in Appendix 2
- e. Visit 13/Day 19 will be the final Induction Phase patch removal - Approximately 30 minutes (up to 1 hour) after removal of the patch, a trained blinded assessor will perform an assessment of all test sites for irritation symptoms using the scoring system detailed in Appendix 2
- f. UVA Irradiation during the Challenge Phase will only be on one of the two the naive patch locations.
- g. Visit 2 (Day 1) Baseline grading/assessments of the patch sites will be performed prior to the patch application.
- h. Final Grading/assessment of irradiation from the Induction Phase will be carried out on Visit 14/Day 22 (first Day of the Rest Phase).
- i. Visit 15 (Day 36) Grading/assessments of each of the naïve challenge patch sites will be performed prior to application of the 2 Challenge patches.
- j. Further evaluations of the naïve patch sites (irradiated and non-irradiated) 24 (± 2), 48 (± 2) and 72 (± 2) hours after the challenge patches are removed.
- k. Subjects are asked to report any adverse events from Visit 2 (or Visit 1 if patch application occurs at Visit 1) and the use of any concomitant medications throughout the study.

	Document Name	Clinical Protocol 207587		
	Type	Version	Document Identifier	Effective Date
	eldo_clinical_doc	2.0; Most-Recent; Effective; CURRENT	090032d580d16e68	24-Mar-2017 07:31:59
	Reason For Issue	Auto Issue		

Patch Schedule

Activity	INDUCTION												REST	CHALLENGE				
	Week 1				Week 2				Week 3				Week 4-5	Week 6				
	MON	TUE	THU	FRI	MON	TUE	THU	FRI	MON	TUE	THU	FRI		MON	TUE	WED	THU	FRI
Application of the 1 st patch	X																	
Removal of the 1 st patch / Assess/UVA Irradiation		X																
Assess 1 st patch/Application of the 2 nd patch			X															
Removal of the 2nd patch / Assess/UVA Irradiation				X														
Assess 2nd patch/Application of the 3rd patch					X													
Removal of the 3rd patch / Assess/UVA Irradiation						X												
Assess 3rd patch/Application of the 4h patch							X											
Removal of the 4th patch / Assess/UVA Irradiation								X										
Assess 4th patch/Application of the 5th patch									X									
Removal of the 5th patch/ Assess/UVA Irradiation										X								
Assess 5th patch/Application of the 6th patch											X							
Removal of the 6th patch/ Assess/UVA Irradiation												X						
Assess Challenge Patch naïve sites (prior to Challenge patch application)														X				
Application of the Challenge patches (2 patches)														X				
Removal of the Challenge patches/Assess/UVA Irradiation (to one challenge patch location)															X			
Evaluation after Irradiation																X	X	X
Dermatologist Assessment	X																	X

 GlaxoSmithKline	Document Name	Clinical Protocol 207587		
	Type	Version	Document Identifier	Effective Date
	eldo_clinical_doc	2.0; Most-Recent; Effective; CURRENT	090032d580d16e68	24-Mar-2017 07:31:59
	Reason For Issue	Auto Issue		

SYNOPSIS FOR STUDY 207587

Brief Summary

A cosmetic product that is freely available to the consumer must be safe when applied under normal or reasonably foreseeable conditions of use. As a general requirement, the safety and compatibility of a new formulation should be confirmed before it is commercialised (Guideline for the Safety Evaluation of Cosmetic Products; Agência Nacional de Vigilância Sanitária, ANVISA, 2012).

Compatibility studies, performed as patch tests, aim to confirm the local tolerance of topical cosmetic products during the first application to the skin, therefore providing assurance that the product is safe for use under maximized conditions (ANVISA, 2012).

Phototoxicity assessments aim to demonstrate the absence of irritation potential of a product when applied to the skin and exposed to ultra violet (UVA) radiation. Photosensitisation assessments aim to prove the absence of allergic potential of a product applied to the skin when exposed to UVA radiation.

In this three-phase phototoxicity-photosensitisation (PT-PA) study, the test material and a positive control of saline solution are applied under a semi-occlusive patch to the upper back of each subject. The first phase of the study is an Induction Phase; a controlled amount of the test product and control product is applied over a defined surface area of skin (amount per unit area), under a semi-occlusive patch. The patch will remain on the skin for 24 (\pm 2) hours during this phase. Following patch removal, the patch site will be exposed to ultraviolet – A (UVA) radiation and re-assessed **24 48** hours later prior to re-application of another semi-occlusive patch (with both the test and control product) to the same site. The Induction phase will last 3 weeks. After a subject completes the Induction Phase they will enter a Rest Phase of 2 weeks' duration, during which no patches will be applied. After the Rest Phase, subjects will return to the clinical site for the Challenge Phase. In the Challenge phase two test patches will be applied to virgin skin areas on each subject's upper back for 24 hours. Following removal of both patches, one of the Challenge patch test sites will be exposed to UVA radiation. Both Challenge patch test sites will be assessed up until 72 (\pm 2) hours later.

The objective of this clinical study is to assess the phototoxicity and photosensitisation potential of a cosmetic test product under exaggerated conditions of use with controlled product application and under supervision of a dermatologist.

 GlaxoSmithKline	Document Name	Clinical Protocol 207587		
	Type	Version	Document Identifier	Effective Date
	eldo_clinical_doc	2.0; Most-Recent; Effective; CURRENT	090032d580d16e68	24-Mar-2017 07:31:59
	Reason For Issue	Auto Issue		

Objective(s) and Endpoint(s)

Objective(s)	Endpoint(s)
Primary	
To determine the photoirritation and photosensitisation potential of a cosmetic facial skin product after repeated patch applications to the skin of healthy subjects.	Trained assessor assessment of local tolerance through visual assessment of cutaneous irritation via the combined dermal response and other effects scores over the induction and challenge phase.
Secondary	
To evaluate the tolerance of a cosmetic facial skin product.	Assessment of frequency and severity of Adverse Events

Study Design

Overall Design
This is an assessor-blinded (single), test site randomised, intra-subject comparison, repeated insult patch test to evaluate the skin irritation and sensitisation potential of a cosmetic facial product, under exaggerated conditions of use with controlled product application and under supervision of a dermatologist.
Day -14 to 0 / Visit 1 - Screening Visit NOTE: Visit 1 and Visit 2 could be combined
The following assessments will be conducted: 
 1. Subject Informed Consent taken 2. Subject demographics collected 3. Medical history details 4. Details of current and concomitant medication collected 5. Fitzpatrick Skin Type Assessment (Appendix 3) 6. Inclusion/Exclusion criteria 7. Dermatologist determination for eligibility to participate in the study (including visual examination of the dorsum scapular region) 8. Subject eligibility
Days 1 to 22 / Visit 2 - Visit 14 - Induction Phase (3 Weeks) NOTE: Visit 1 and Visit 2 could be combined

 1. The following assessments will be conducted: 2. Continued eligibility check 3. Current/Concomitant Medications review 4. Inclusion/Exclusion criteria review (Inclusion criteria 3c (only) at Visit 2, if Visit 1 and 2 are not combined). 5. Dermatologist determination for continued eligibility to participate in the

 GlaxoSmithKline	Document Name	Clinical Protocol 207587		
	Type	Version	Document Identifier	Effective Date
	eldo_clinical_doc	2.0; Most-Recent; Effective; CURRENT	090032d580d16e68	24-Mar-2017 07:31:59
	Reason For Issue	Auto Issue		

- study (Visit 2/Day 1 only - if visits not combined)
6. Test Site Designation and Randomisation (Visit 2/Day 1 only)
 7. Baseline grading/assessment of test sites (Per Appendix 2) (Visit 2/Day 1 only)
 8. Patch applications (6 patch applications every Monday and Thursday, for 3 consecutive weeks).
 9. Patch removal 24 (\pm 2) hours after application (Tuesday and Friday). Reaction grading/assessment performed by a qualified staff member (24 \pm 2 hours after application). Grading/assessments will be 30 minutes (up to 1 hour) after each patch removal (per Appendix 2)
 10. Application site exposed to UVA irradiation.
 11. ~~24~~ **48** (\pm 2) hours after each UVA irradiation (or 72 (\pm 2) hours, in case of irradiation on Fridays), the sites will be evaluated for signs of dermatological reactions, according to Appendix 2.
 12. Adverse event assessment

*NOTE: Subjects will report to the study site 12 times during the Induction Phase (6 patch applications and removals) **AND ONCE FOR FINAL INDUCTION PHASE PATCH GRADING/ASSESSMENT ON THE FIRST DAY OF THE REST PHASE (VISIT 14/DAY 22)**. No Patch Applications from Days 22 to 35 (Rest Phase).*

Days 22 - Day 35 / Visit 14 -Visit 15 – Rest Phase (2 Weeks)

No Patch Application

Days 36 to 39 / Visit 15-Visit 18 – Challenge Phase

The following assessments will be conducted:

1. Continued eligibility check
2. Current/Concomitant Medications review
3. Grading/assessment of naïve challenge patch sites performed by a qualified staff member (per Appendix 2) prior to Challenge patch application (Visit 15/Day 36).
4. Challenge Patch application, 2 patches to naïve sites (Visit 15/Day 36).
5. Patch removal 24 (\pm 2) hours later (Visit 16/Day 37).
6. Reaction grading/assessment performed by a qualified staff member 30 minutes (maximum 1 hour) after patch removal (Visit 16/Day 37).
7. One of the naïve patched sites will be exposed to 5 Joules per square centimeter (J/cm^2) UVA radiation.
8. Subjects will return for grading/assessment performed by a qualified staff member 24 (\pm 2) hours after UVA irradiation (Visit 17/Day 38). Both irradiated non non-irradiated sites will be assessed.

	Document Name	Clinical Protocol 207587		
	Type	Version	Document Identifier	Effective Date
	eldo_clinical_doc	2.0; Most-Recent; Effective; CURRENT	090032d580d16e68	24-Mar-2017 07:31:59
	Reason For Issue	Auto Issue		

9. Subjects will return for grading/assessment performed by a qualified staff member 48 (\pm 2) hours after UVA irradiation (Visit 18/Day 39). Both irradiated non non-irradiated sites will be assessed.
 
10. Adverse event assessment.

Day 40 / Visit 19 – End of Study

The following assessments will be conducted:
 
 1. Current/Concomitant Medications review 2. Adverse event assessment. 3. Subjects will return for grading/assessment performed by a qualified staff member 72 (\pm 2) hours after UVA irradiation (Visit 19/Day 40). Both irradiated non non-irradiated sites will be assessed. 4. Dermatologist final assessment 5. Subject discharge from the study site following completion of all study procedures.

Type and Planned Number of Subjects

Approximately 40 healthy subjects will be screened to randomise at least 30 subjects to ensure at least 25 evaluable subjects complete the entire study. This sample size is standard in clinical testing practices and is consistent with the ANVISA guidelines (ANVISA, 2012).

Diagnosis and Main Criteria for Inclusion

Healthy male and female volunteers aged 18 to 65 with no dermatological disorders, with a Fitzpatrick skin phototype II to IV will be enrolled into this study.

Product Information

	Test Product	Reference Product
Product Name	Facial micellar cleanser	Saline Solution: Sodium Chloride (NaCl; 0.9%)
Product Formulation Code (MFC)	CCI [REDACTED]	N/A Site to supply
Product Format	200ml clear PET Bottle	N/A
Application Quantity	0.02 millilitres per square centimetre (ml/cm ²)	0.02 ml/cm ²
Route of Administration	Topical application via semi occlusive patch	

 GlaxoSmithKline	Document Name	Clinical Protocol 207587		
	Type	Version	Document Identifier	Effective Date
	eldo_clinical_doc	2.0; Most-Recent; Effective; CURRENT	090032d580d16e68	24-Mar-2017 07:31:59
	Reason For Issue	Auto Issue		

Application Instructions	Applied on-site by technician
---------------------------------	-------------------------------

Statistical Methods

The focus of the statistical analysis will be the evaluation of the frequency and level of irritation and sensitisation responses of the investigational product. All subjects with any product applied will be included in the analysis population.

Individual observations will be assessed based on Appendix 2 and a narrative description of all skin responses, both in the induction and challenge phases, will be provided. A frequency tabulation of the number of subjects with any skin response versus those without any skin response will be presented by treatment for both the induction and challenge phases of the study. If there are subjects with non-zero dermal response or superficial irritation scores, a combined dermal and others effects score will be determined across all time points over the induction and challenges phases as well as at each assessment time point and summarised using descriptive statistics.

No interim or subgroup analyses are planned.

Adverse Events (AE) will be tabulated according to the current version of the Medical Dictionary for Regulatory Activities (MedDRA). Frequencies and percentages will be presented overall, for each system organ class, and for each preferred term. Summaries of treatment-emergent AEs, treatment-related AEs, AEs leading to discontinuation, and serious AEs will be completed. For treatment-related AEs, these will also be presented by treatment /test site.

Detailed methodology for summary and statistical analyses of the data collected in this study will be documented in a Statistical Analysis Plan, which will be maintained and signed off prior to study unblinding.

 GlaxoSmithKline	Document Name	Clinical Protocol 207587		
	Type	Version	Document Identifier	Effective Date
	eldo_clinical_doc	2.0; Most-Recent; Effective; CURRENT	090032d580d16e68	24-Mar-2017 07:31:59
	Reason For Issue	Auto Issue		

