2. OBJECTIVE(S) AND ENDPOINT(S)

Objective(s)	Endpoint(s)
Primary	
To determine the photoirritation and photosensitisation potential of a cosmetic facial skin product after repeated patch applications to the skin of healthy subjects.	Trained assessor assessment of local tolerance through visual assessment of cutaneous irritation via the combined dermal response and other effects scores over the induction and challenge phase.
Secondary	
To evaluate the tolerance of a cosmetic facial skin product.	Assessment of frequency and severity of Adverse Events

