9. STATISTICAL CONSIDERATIONS AND DATA ANALYSES

9.1 Sample Size Determination

Approximately 40 healthy subjects will be screened to randomise at least 30 subjects to ensure at least 25 evaluable subjects complete the entire study. This sample size is standard in clinical testing practices and is consistent with the ANVISA guidelines (ANVISA, 2012).

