9.3.2. Primary Analysis(es)

The primary analysis will be based on the irritation (dermal response) and superficial irritation (other effects) scores/grades assessed using the scales described in Tables 1 and 2 of Appendix 2. Individual observations will be assessed based on these scales and a narrative description of all skin responses, both in the induction and challenge phases, will be provided.

No formal statistical inference will be performed.

The number and percentage of subjects recording each category of score/grade, as well as any skin response versus those without any skin response will be presented by treatment group at each assessment time point and over the induction and challenge phases using the maximum grade/score across time points. If there are subjects with non-zero dermal response or other effects scores, then the dermal response, other effects and a combined dermal and others effects score will be summarised using descriptive statistics at each assessment time point and over the induction and challenges phases using the total score across time points.

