BURNS MODERATELY; TANS GRADUALLY (LIGHT BROWN SKIN)	XX (XX.X)	XX (XX.X)	XX (XX.X)
BURNS MINIMALLY, ALWAYS TANS WELL (MODERATE BROWN SKIN)	XX (XX.X)	XX (XX.X)	XX (XX.X)
RARELY BURNS, TANS PROFUSELY (DARK BROWN SKIN)	XX (XX.X)	XX (XX.X)	XX (XX.X)
NEVER BURNS (DEEPLY PIGMENTED DARK BROWN TO BLACK SKIN)	XX (XX.X)	XX (XX.X)	XX (XX.X)

Page x of y

PPD

PPD

PROTOCOL: 207587

PROGRAM RUN DATE: DDMONYYYY

TABLE 14.2.1.1
FREQUENCY OF COMBINED SCORE BY PHASE, VISIT AND TREATMENT AND MAXIMUM COMBINED SCORE

STUDY POPULATION: INTENT TO TREAT POPULATION (N=XX)

PHASE: INDUCTION PHASE

VISIT	COMBINED SCORES	FACIAL MICELLAR CLEANSER (N=XX) N	SALINE SOLUTION (N=XX) N
SUBJECTS WITH AT LEAST ONE COMBINED SCORE > 0 AT ANY VISIT N (%)		XX (XX.X)	XX (XX.X)
SUBJECTS WITH NO COMBINED SCORE > 0 AT ANY VISIT N (%)		XX (XX.X)	XX (XX.X)
VISIT 2	0	XX	XX
	1	XX	XX
	2	XX	XX
	3	XX	XX
	4	XX	XX
	5	XX	XX
	6	XX	XX
	7	XX	XX
VISIT 3		XX	XX
		XX	XX
		XX	XX
VISIT 13		XX	XX
		XX	XX
MAXIMUM COMBINED SCORE	1	XX	XX
	2	XX	XX
	3	XX	XX
	4	XX	XX
	5	XX	XX
	6	XX	XX
	7	XX	XX

COMBINED SCORE: DERMAL RESPONSE SCORE + SUPERFICIAL RESPONSE SCORE (>0)

PAGE X OF Y

PPD

PPD

Programming Note:

- Induction Phase include Visit 2 (Visit 1 and Visit 2 could be combined) till Visit 13.

- Rest Phase include Visit 14
- Challenge Phase include Visit 15 till Visit 19.
- This table is only required if at least one subject reports a combined score >0
- Maximum combined Score will be calculated and displayed at the end of each phase irrespective of visits.

PROTOCOL: 207587

PROGRAM RUN DATE: DDMONYYYY

TABLE 14.2.2.1
FREQUENCY OF DERMAL RESPONSE SCORE BY PHASE, VISIT AND TREATMENT AND MAXIMUM DERMAL RESPONSE SCORE

STUDY POPULATION: INTENT TO TREAT POPULATION (N=XX)

PHASE: INDUCTION PHASE

VISIT	FACIAL MICELLAR CLEANSER		SALINE SOLUTION	
	(N=XX)	N	(N=XX)	N
SUBJECTS WITH AT LEAST ONE DERMAL RESPONSE	XX (XX.X)		XX (XX.X)	
SCORE > 0 AT ANY VISIT N (%)				
SUBJECTS WITH NO DERMAL RESPONSE SCORE > 0 AT ANY VISIT N (%)	XX (XX.X)		XX (XX.X)	
VISIT 2	SCORE=0	XX		XX
	SCORE=1	XX		XX
	SCORE=2	XX		XX
	SCORE=3	XX		XX
	SCORE=4	XX		XX
	SCORE=5	XX		XX
	SCORE=6	XX		XX
	SCORE=7	XX		XX
VISIT 3			
VISIT 4	...			
.....				
VISIT 13	...			
.....				
MAXIMUM DERMAL RESPONSE SCORE			

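### If every score is zero, the SAP lets the report omit the primary frequency table that the protocol promises unconditionally, and no planned output says what zero reactions can exclude

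*Protocol*

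**What the plan says.** **Protocol.** Section 9.3.2 promises counts and percentages for each grade "as well as any skin response versus those without any skin response will be presented by treatment group at each assessment time point", and also over each phase. The Synopsis (Statistical Methods) makes the same promise by treatment for Induction and Challenge. In both places only the descriptive statistics depend on a non-zero score. Sections 3.4 and 6.2.2 add that results will be shown as individual responses for each product at every time point.

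**SAP.** Section 2.4.1.1 limits the combined-score summary to subjects who score above zero at some visit. The programming note to the Table 14.2.1.1 shell reads: "This table is only required if at least one subject reports a combined score >0". The Table 14.2.2.1 shell carries a parallel note for the dermal response score; the Table 14.2.2.2 shell has none. Section 4.3 names five listings, none of them of skin scores, and its rule on null output concerns listings. Section 3 declares that nothing departs from the protocol's planned analysis.

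**Inference and sample size.** Protocol 9.3.2 and SAP 2.4.1.1 rule out formal inference, and SAP 2.4.1.2 marks hypothesis and model as not applicable. No confidence interval appears in the text or the table shells. Protocol 9.1 plans "to randomise at least 30 subjects to ensure at least 25 evaluable subjects complete the entire study" and gives as its reason: "This sample size is standard in clinical testing practices and is consistent with the ANVISA guidelines".

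**Aim.** The Synopsis (Brief Summary) and the SAP introduction say: "Photosensitisation assessments aim to prove the absence of allergic potential". The primary objective, in Protocol section 2 and SAP 1.2, is "To determine the photoirritation and photosensitisation potential of a cosmetic facial skin product".

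**The concern.** A result with no reactions is only as informative as the number of subjects in whom a reaction could have been seen. That is the result for which the SAP requires the least output.

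The denominator is not obvious from other figures. ITT membership needs a score from only one test site (Protocol 9.2.1), withdrawals are not replaced (4.5) and missing scores are not imputed (9.2.4). An ITT count of 30 is therefore compatible with 25 or fewer subjects graded at Challenge, the phase on which photosensitisation is judged.

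An all-zero result is possible. Protocol 3.4 disregards the expected UVA erythema and pigmentation, with saline as the standard, and the exclusion criteria remove people with atopy, earlier sensitisation in a patch study or abnormal reactions to sun. If it happens, a statement of no reactions could be reported without its denominator and without any indication of the rates it leaves open.

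**Working it through.** **1. The two commitments compared.**

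- Protocol 9.3.2 and Synopsis: the response versus no-response tabulation has no condition attached.
- SAP 2.4.1.1: subjects without a positive combined score drop out of the summary.
- SAP shells 14.2.1.1 and 14.2.2.1: the table is needed only if at least one positive score occurs.
- SAP section 3: no change declared.

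The SAP is also at odds with itself. The Table 14.2.1.1 shell has a row for subjects with no positive score and a score-0 row at each visit, which the restriction in 2.4.1.1 would leave empty.

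**2. What survives if all scores are zero.**

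- Table 14.1.1: randomised, completer and ITT counts, but not the number graded per visit.
- Tables 14.2.1.1 and 14.2.2.1: may be omitted.
- Table 14.2.2.2: not conditional. However, Protocol 3.4 records a superficial score only when the dermal score is above zero, so the table would have little or nothing to count.
- Listings: none contains scores.
- Narratives: Protocol 3.4 provides them for scores above zero, so there would be none.

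**3. The plan's own figure.** Thirty randomised and 25 evaluable imply a loss of 5/30 = 16.7%, and 25/(1 − 1/6) = 30. No dropout rate, reaction rate, margin, alpha or power is stated. The sample size therefore has no formula to reproduce and does not say what zero reactions should exclude.

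**4. What zero reactions exclude.** Inputs: n = 25 and n = 30 from Protocol 9.1. The confidence level is an assumption, because the documents name none. With no events, the exact (Clopper-Pearson) upper limit U solves (1 − U)^n = α, so U = 1 − α^(1/n). Take α = 0.05 for one-sided 95% and α = 0.025 for the upper end of a two-sided 95% interval.

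| Result | One-sided 95% | Two-sided 95% |
|---|---|---|
| 0/25 | 1 − 0.05^(1/25) = 11.3% | 1 − 0.025^(1/25) = 13.7% |
| 0/30 | 1 − 0.05^(1/30) = 9.5% | 1 − 0.025^(1/30) = 11.6% |

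**5. Illustration at an assumed true rate of 5%** (a rate not in the documents). The chance of seeing no reaction is 0.95^25 = 27.7% with 25 subjects and 0.95^30 = 21.5% with 30. To bring the one-sided 95% limit below 5% with zero events would need ln(0.05)/ln(0.95) = 58.4, so 59 subjects.

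**The case against.** **Omission is allowed, not ordered.** The shell notes say when a table is needed; they do not forbid printing it otherwise. Table 14.2.1.1 is also in the top-line outputs (SAP 4.4) without a condition. This stands: one cannot say that the table will be missing, only that the SAP permits it.

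**The trigger is easily met.** One positive score in any subject is enough, the notes limit it to neither product nor phase, and a score of 1 is barely perceptible erythema. Once triggered, the shell shows responders, non-responders and score-0 counts. This stands as a limit on how often the gap would matter. The documents give no basis for estimating the chance of an all-zero study.

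**No inference was promised.** Leaving out an interval breaks no commitment, and a reader could derive one from N. The first half stands. The second half needs the number graded, which is the figure at risk. A descriptive limit tests no hypothesis, so it does not conflict with the plan.

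**A stronger reading to avoid.** A reader might infer from "Photosensitisation assessments aim to prove the absence of allergic potential" that this trial undertakes to prove absence and is too small to do so. The documents do not support that. The sentence is background on assessments of this kind, while the objective is to determine the potential and the plan openly disclaims inference.

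**An any-response limit would mislead.** Protocol 3.4 bars pre-UVA reactions and reactions at the non-irradiated Challenge site from judging photoirritation or photosensitisation. A single limit on an any-response row would mix these with irradiated-site scores. This stands and shapes the fix.

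**Conclusion.** The point holds as a mismatch between protocol and SAP that should be corrected. The protocol's tabulation is unconditional, the SAP makes it conditional and narrows who is summarised, and the SAP declares no change. In an all-zero study the primary frequency table and the numbers graded per visit and at Challenge may go unreported. The overall ITT and completer counts would still appear.

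The size of what is left unsaid rests on the assumed level and on the number graded. At one-sided 95%, true rates up to 11.3% (25 graded) or 9.5% (30 graded) are not excluded; at two-sided 95% the figures are 13.7% and 11.6%. These limits treat subjects as independent and apply only if no reaction occurs.

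The missing limit is a weakness of reporting, not a breach of the plan. Nothing here shows that the sample size fails a criterion, since the documents set none.

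**What to change.** 1. Delete the restriction in SAP 2.4.1.1 and the conditional notes on Tables 14.2.1.1 and 14.2.2.1. Always print both tables and Table 14.2.2.2, with the number graded per visit and phase for each product. If the sponsor prefers to keep the condition, SAP section 3 should declare it as a change from the protocol.
2. For each product, add an exact (Clopper-Pearson) upper limit at a stated confidence level, labelled as descriptive. Calculate it for post-irradiation scores (Induction Visits 4, 6, 8, 10, 12 and 14; irradiated Challenge site, Visits 17 to 19) separately from pre-UVA and non-irradiated scores. The shells have product columns only, so a split by irradiation must be added. Visit 14, which the Table 14.2.1.1 note assigns to the Rest Phase, must be counted with the Induction irradiations.
3. Quote the denominator and the limit with any statement that no reactions occurred.
4. Optionally, soften the background sentence on proving absence in the Synopsis and the SAP introduction.

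The cost is slightly more table work and a less favourable-looking statement. No extra subjects, data or hypothesis test are needed.
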